5.2.3 Follow-up Assessments (3, 6, 9, and 12 months)

In-person follow-up assessments will be prioritized around the participant’s clinical appointments. UW study staff will contact the participant to complete assessments prior to their scheduled blood draw/fecal specimen collection. This outreach will include a combination of phone, mail, and email as determined by the contact information provided by the participant. If a participant hasn’t completed their scheduled follow up assessment at the time of their visit, the study staff will attempt to complete it in person. The follow-up assessments are listed in detail in Table 1.

In addition to the survey assessments, participants’ specimens will be collected at 6 and 12 months following the same guidelines as in the baseline visit. Specimen collection will coordinate with clinical appointments whenever possible.

See section 5.2.1 for specimen collection instructions, which remain the same for follow-up time points. Participants will be reminded that they are welcome to contact their research coordinator at any time if any questions or concerns should arise. UW study staff will communicate with the research coordinator to ensure appropriate reporting is completed should an AE or complication be reported to them.

Self-reported complications or AEs will be recorded. Any serious adverse events (SAEs) will be communicated to the relevant site study team to ensure appropriate reporting is completed.

5.2.7 Participant Burnout and Optimizing Data Collection

Participants may experience research assessment burnout due to the frequency and number of questions asked of them. To optimize complete data collection, research personnel should recognize a participant's reluctance to complete the research assessment and request that the participant instead complete a sub-set of survey responses (minimal research assessment). In the event that a participant prefers to complete a minimal research assessment, research personnel should prioritize asking the research participant questions related to signs and symptoms of diverticulitis and aim to complete the Food Frequency Questionnaires. Study staff will be provided with a prioritization model to clarify what questions are high versus medium priority. Study staff should use their best judgment to determine how many additional survey questions should be asked. It is preferred to miss some responses at one research assessment time point rather than risk the participant withdrawing altogether due to research assessment burnout.

5.3 Medical Record Review

Time points

Participants will have their EMR reviewed at ad-hoc time points if triggered by a survey response or if they have a diverticulitis event. Study staff will conduct an EMR review to assess the following:

1. Complications for patients using the National Surgical Quality Improvement Program (NSQIP) definitions and protocol; and
2. The following information related to diverticular disease:
 - a. Indication for healthcare utilization
 - b. Length of stay (if hospitalized);
 - c. Surgery type, if applicable.

As needed, chart review will be conducted if a patient reports an adverse event and further documentation is needed.

Data Collection

Data will be collected using the following forms:

| Form | Description |
|-------------|--------------------|
|-------------|--------------------|

| | |
|-----------------------------|--|
| Form Information | Captures information about when the form was filled out (time point), and by whom |
| Enrollment Form | Completed at index visit only; captures basic demographics and treatment assignment data; medical history and cohort designation |
| Healthcare Utilization Form | Captures information about any visit (date, setting, treatments, medications) |
| Adverse Events Form | Captures information about adverse events at any time point |

If a participant seeks care at an outside hospital, the study team will work with the participant to obtain relevant information.

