6.0 Outcome Assessments

6.1 Primary and Secondary Outcomes

Patient Reported Outcomes (PROs) will be assessed for adults using both generic and disease-specific surveys utilizing the QoL instruments in Table 2.

Table 2. Primary and secondary outcomes and intervention related process measures.

| Primary or Secondary | Name of Outcome | Specific Measure to Be Used | Time Point |
|----------------------|---|--|------------------------|
| Primary | Willingness to enroll | Enrolled/approached | Baseline |
| Primary | Adherence to USDA Med-Style Food Pattern | USDA Med-style Pattern score calculated from the NASR FFQ. ¹⁶¹ | Baseline, 6, 12 months |
| Primary | Participant retention | Proportion enrolled and retained at 3, 6, 9 and 12 months | 3, 6, 9 and 12 months |
| Primary | Interaction with on-line program | Number of times accessed | Bi-weekly |
| Primary | Engagement with nutrition services | Number of sessions with dietician | Quarterly |
| Secondary | Plasma, IL-6, IL-10, IL-1 β , fecal calprotectin | Concentration | Baseline, 6, 12 months |
| Secondary | Diverticulitis events | Self-reported (presumed), subset of those resulting in healthcare utilization (e.g., hospitalization, surgery). | Quarterly |
| Secondary | NSQIP-defined complications, a subset of which are serious adverse events to be reported to ISM | Standardized assessment-serious events defined as death, cardiac arrest, myocardial infarction, pneumonia, progressive renal insufficiency, acute renal failure, pulmonary embolism, deep vein thrombosis, return to operating room, serious site infections | Quarterly |
| Secondary | DVQOL ⁶⁵ | A 17-item questionnaire that assesses four domains: symptoms, concerns, emotions, and behavior changes related to diverticulitis. | Baseline, 6, 12 months |
| Secondary | GIQLI ¹⁵⁹ | A 36-item questionnaire that assesses five domains: gastrointestinal symptoms, physical function, emotional well-being, social well-being, and perception of medical treatment measured by a single item question. | Baseline, 6, 12 months |

| | | | |
|-----------|--------------------------------|--|------------------------|
| Secondary | IPAQ Short Form ¹⁶⁹ | A validated 7-item questionnaire: moderate and vigorous physical activity, walking, and sitting in the past 7 days | Baseline, 6, 12 months |
| Secondary | Time in healthcare | Days missed from work/school, ED/hospital encounters, diverticulitis-related diagnostic/therapeutic interventions | 3, 6, 9 and 12 months |

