6.2 Clinical Complications

Death, SAEs, and complications (reported as AEs via EMR review) will be assessed and recorded through the study surveillance period. Complications (reported as AEs) will incorporate NSQIP standards and definitions as well as events related to antibiotic-related complications.

Table 3: Summary of SAE/AEs

| Serious Adverse Events | Adverse event |
|--|--|
| Death | |
| Life-threatening event | |
| CVA or stroke | |
| MI requiring treatment or cardiac arrest | Myocardial infarction Atrial arrhythmia |
| Unplanned admit to ICU | |
| Acute Renal Failure (requiring dialysis) | Major UTI (e.g., pyelonephritis) Urinary retention Acute Renal Failure (no dialysis) Progressive renal insufficiency |
| C. difficile colitis (requiring colon resection) | |
| Pulmonary embolism requiring therapy | DVT/PE requiring treatment |
| Coma >24 hours | |
| Septic shock (requiring pressors) | Sepsis |
| Bleeding requiring transfusion | |
| Newly infected prosthetic graft infection | |
| Mechanical ventilation >48 hours | Tracheal reintubation/tracheostomy |
| Colostomy or ileostomy | NG tube replacement (non-routine) Bowel obstruction Ileus |
| | Organ/space infection (including peritonitis) Surgical site infection Intra-ab Abscess Severe dehydration Hernia Malignant hyperthermia Pneumonia Other infection Other post-op occurrence: unspecified Other non-operative intervention: unspecified Unplanned (re)operative intervention during index C. difficile colitis (not requiring colon resect) |

| | |
|------------------------------|--|
| Other life threatening event | |
| Hospitalization* | |

*Exception to hospitalizations that do not need to be reported as an SAE:

- Planned, elective surgical procedures
- Labor and delivery
- Psychiatric hospitalizations

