7.1.2 Data Quality Monitoring

The CCC and DCC will review participant enrollment, reasons for exclusion, participant demographics, and follow-up rates by site in order to assess proximity to enrollment targets, site performance, and protocol adherence.

The DCC will perform in-line quality assurance checks by using field masking, range checks, and real-time warning messages. Missing data reporting and other customized reports will be developed by the DCC in collaboration with the CCC and recruitment team in order to facilitate efficient work-flow and high-quality data capture. A subset of key personnel from the DCC and CCC will serve as an operations committee and review quality control reports on a weekly or biweekly basis, though quality control reports will be made available on a daily basis. CRF-specific follow-up rates will be tabulated on a nightly basis and reviewed during the weekly check-in meeting with each clinical recruitment site. Nightly, the DCC will generate graphs that monitor CRF-specific follow-up rates over time as well as data quality trigger rates over time to prospectively monitor potential issues that may develop gradually or acutely over time. A data query resolution dashboard will be available to each site on a continuous basis. In similar studies, we have found that establishing a fixed-day for a monthly review of all unresolved queries is an adequate balance of time to resolution and alert fatigue.

On a nightly basis, the DCC will also generate a comprehensive data quality report to flag unusual data and will be made broadly available to the study team. Research staff at the recruitment sites will be asked to review each outstanding query and respond with “confirmed” or “corrected” and may provide a comment beside each query to note relevant details. Each query will be closed by the DCC protocol operations specialist.

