8.5 Secondary Statistical Analyses

Binary and categorical endpoints (e.g., adverse events and complications) will be tabulated by intervention group. Time in healthcare will be summarized by group using medians and interquartile ranges, and differences between intervention groups will be summarized using 95% confidence intervals generated from generalized linear regression models appropriate for each type of outcome (e.g., binary, count, continuous, etc.). To examine the sensitivity of adherence to the Med-style Food Pattern on changes in serum biomarkers, we will modify the primary analytic model described for Aim 2 by separately adjusting for a binary indicator of adherence (adherent vs. not) and a graded measure of adherence to intervention. Finally, we will use

mediation analyses to explore the extent to which changes in serum biomarkers over time are mediated through intervention-induced changes in weight and physical activity.

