8.6 Missing Data

Participants who do not complete some or all of the baseline and follow-up questions will have missing data points. As summarized in the NEJM guidance,¹⁶³ we will employ three primary strategies that are recommended to address missing data. First, the DCC will work in conjunction with the CCC to minimize the amount of missing data since prevention of missing data is preferable to any attempted analysis correction. We will document all reasons for missing data. Second, we will use inverse probability weighting¹⁶⁴ to inflate the weights of cases that are under-represented in the analysis due to selective attrition and/or non-participation. A descriptive analysis that characterizes enrolled participants who do not provide data due to attrition will be conducted, and we will use observed covariates to construct a weighted model using logistic regression. Third, the strategy that we used for two recent primary trial publications^{102, 165} and which we will adopt for our primary analysis is the use of 10-fold multiple imputation to assess the robustness of the results when missing data are imputed and allowing all participants to be included in intent-to-treat analysis. Our primary approach is to use multiple imputation since it provides flexibility in inclusion of relevant baseline and follow-up data. We will also impute missing data under both pessimistic and optimistic scenarios to provide bounds on the statistical uncertainty.

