9.0 Study Related SAEs

9.1 Identification of SAEs

Randomized participants will be monitored for SAEs throughout their study surveillance period (enrollment through twelve months). The occurrence of an SAE may come to the attention of study personnel during study follow-up phone interview or by a study participant calling the study team or presenting for medical care. Study staff will use the EMR to fill out the SAE form. The PI will then complete the form and sign the form. The SAE form will then be submitted to the DCC who will provide it to the ISM. The ISM will review the SAE form and ask the study team for additional clarification or specification as he/she sees necessary.

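### Section 8.1 claims blinded data collection that the written procedures do not deliver; as a minor point, charts are opened only on a trigger, so complications in silent participants can go unseen

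*Combined protocol and SAP*

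**What the plan says.** **Blinding.** Section 8.1 leaves participants unblinded but says that the investigator team and the research staff who collect data do not know the arm. It also says that research coordinators randomise through a web portal that gives them the next assignment. Section 5.1 has coordinators, or other study team members, offer the baseline and follow-up assessments. In Section 5.2.2 only the Medi For All arm is prompted for a bi-weekly MEDAS score, and study staff pursue those who miss it. In Section 5.2.3 UW study staff make the follow-up contact and pass any reported event to the coordinator.

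**Event capture.** Table 2 in Section 6.1 lists "NSQIP-defined complications, a subset of which are serious adverse events to be reported to ISM" as a quarterly secondary outcome. Section 6.2 says that "complications (reported as AEs via EMR review) will be assessed and recorded through the study surveillance period". Section 9.1 commits to SAE monitoring of randomised participants from enrolment to twelve months, and says SAEs may come to light "during study follow-up phone interview or by a study participant calling the study team or presenting for medical care". On when a chart is opened, Section 5.3 says: "Participants will have their EMR reviewed at ad-hoc time points if triggered by a survey response or if they have a diverticulitis event". It adds chart review, as needed, after a participant-reported adverse event. No section schedules a review for everyone.

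**Analysis.** Section 8.5 says: "Binary and categorical endpoints (e.g., adverse events and complications) will be tabulated by intervention group". It gives no denominator. Section 8.6 says: "Participants who do not complete some or all of the baseline and follow-up questions will have missing data points". It then provides multiple imputation as the primary approach, inverse probability weighting, and pessimistic and optimistic scenarios.

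**The concern.** On blinding, one named role both receives the assignment and may collect outcomes. A report that repeats Section 8.1 would tell readers that data collection was masked when the procedures do not ensure it.

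On event capture, the record is the stated source for complications, but a chart is opened only after something has been reported or noticed. A participant who stops answering gives no survey trigger. Death is the clearest case: it is a listed SAE (Table 3 and Section 9.2), yet a participant who has died cannot return the survey that would prompt review. The table of complications by arm could then be incomplete, and its footing for unreviewed participants would be unclear. These are secondary outcomes in a feasibility pilot without formal testing, so no efficacy conclusion is at stake. However, the pilot is meant to prepare a larger trial on recurrence and complications (Section 3.1), so workable event capture is part of what it should show.

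**Working it through.** **1. Blinding: the sections side by side**

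- Who sees the arm: research coordinators, through the portal (8.1). The Enrollment Form in 5.3 also records the assignment.
- Who may collect follow-up data: research coordinators or study team members (5.1).
- Who is said to be blinded: research staff who collect data (8.1).

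The coordinator appears in the first two lines, so the third cannot hold as written unless coordinators who randomise are kept out of follow-up collection. No section does that. Section 5.2.2 is weaker support, since the staff who chase MEDAS scores could be a separate team. Section 5.2.3 suggests a separate UW team but does not say that it is masked.

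**2. Event capture: what is covered and what is left**

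- Adverse events and diverticulitis symptoms with healthcare use are survey items at 3, 6, 9 and 12 months in both arms (Table 1). If unanswered, they are missing under 8.6.
- Diverticulitis events are self-reported (Table 2), so the same applies.
- What is left is record-based information in charts never opened: NSQIP-defined complications, SAEs including death, and details of healthcare use. Section 8.6 is written around unanswered questions and does not say how to class these.

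**3. Size, under assumptions**

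The plan has no figure to reproduce on this point. The documents give N = 50 + 25 = 75 but no complication rate and no expected non-response. Let *p* be the 12-month risk and *s* the fraction silent. Assume equal risk in silent and responding participants, and that no event in a silent participant surfaces by another route; the second assumption overstates the loss.

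Expected missed events = 75 × *p* × *s*, with *s* from 10% (75 × 0.10 = 7.5 people) to 30% (75 × 0.30 = 22.5 people).

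| Assumed risk | Lowest | Highest |
|---|---|---|
| 1–3% | 75 × 0.01 × 0.10 = 0.08 | 75 × 0.03 × 0.30 = 0.68 |
| 10–20% | 75 × 0.10 × 0.10 = 0.75 | 75 × 0.20 × 0.30 = 4.5 |

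The first row fits better the statement in 9.2 that life-threatening complications or SAEs are a very rare possibility in both arms. The second row is a high-end sensitivity range. Expected losses reach one event only when *p* × *s* reaches 1/75 = 0.0133, that is *p* = 13.3% with 10% silent, or *p* = 4.4% with 30% silent.

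**4. Effect on the comparison of arms**

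If unreviewed silent participants were counted as event-free, the expected reported rate would be *p*(1 − *s*). With equal *s* in both arms, equal risks stay equal. A spurious gap needs unequal silence. With 10% silent in one arm and 30% in the other, the gap is 0.20 × *p*: 0.6 points at *p* = 3% (2.7% against 2.1%) and 4 points at *p* = 20% (18% against 14%). Its direction depends on which arm is quieter. If silent participants are treated as missing and silence is unrelated to risk, the expected gap is zero.

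**The case against.** **On event capture**, the case against is substantial. Quarterly surveys collect adverse events and healthcare use in both arms. Section 8.6 covers participants who answer nothing as well as those who skip items, and adds weighting, imputation and bounding scenarios. Retention is itself a primary outcome in Table 2, and Section 7.1.2 says "CRF-specific follow-up rates will be tabulated on a nightly basis", so the study will know who was silent. Section 5.2.7 puts diverticulitis questions first for reluctant participants, and Section 5.7.1 gathers alternate contacts. All of this stands. A reader might infer that the plan ignores non-responders altogether; Section 8.6 shows that it does not. What remains is the unopened chart: alternate contacts serve to update contact details, and the routes in 9.1 other than the scheduled interview rely on the participant calling or seeking care.

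A reader might also infer that the comparison of complications is biased between arms, since only one arm has bi-weekly prompts and outreach. The documents do not support this. They give no non-response by arm, and the quarterly surveys are the same in both.

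**On blinding**, Section 5.1 allows study team members in place of coordinators, Section 5.2.3 points to separate UW staff, baseline should be completed before the assignment is revealed (5.2.1), and most outcomes are self-reports or assays. It would therefore go too far to infer that unblinded coordinators will in fact collect the outcomes, or that results are distorted. The objection does not rescue the statement in 8.1, because a possible division of roles is not a stated one.

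**Conclusion.** The blinding statement in 8.1 is wrong as written and should be corrected. The conflict between 8.1 and 5.1 is enough to establish this. Its consequence is an inaccurate claim in the report, and no effect on results is quantified.

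The event-capture point holds as a minor, inexpensive improvement, limited to record-based events in participants whose charts are never opened. Its size is unknown. At an assumed risk of 1–3%, the expected loss is below one event in 75 participants. The larger figures need a 10–20% risk that the documents do not give for complications, and every figure assumes that nothing surfaces through the other routes in 9.1. The missing denominator in 8.5 is, on its own, largely a matter of detail, because 8.6 already supplies the machinery.

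**What to change.** **Blinding.** Reconcile 8.1 with 5.1, 5.2.2 and 5.2.3 in one of two ways. Either keep staff who randomise, or who do outreach specific to one arm, out of follow-up outcome collection; or limit the statement in 8.1 to roles that do not see the assignment, for example laboratory staff if they are masked. The first makes coordinator staffing less flexible. The second costs a sentence.

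**Event capture.** Add to 5.3 one close-out record review at 12 months, or at the last date that consent permits, for every randomised participant in both arms, by existing staff on the existing Healthcare Utilization and Adverse Events forms. Keep self-reported diverticulitis events as their own outcome. State in 8.5 that 8.6 applies to the record-based endpoints: a participant with neither a survey nor an accessible chart for a period is missing, and the number of such participants is reported by arm.

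The cost is at most 75 chart reviews, or 37.5 to 75 staff hours if each takes 30 to 60 minutes (an assumption). Care outside accessible records, including that of website enrolees who need no clinic visit, would still depend on participant report. Review after withdrawal depends on the consent text, which is not in the copy reviewed; 5.5.1 rules out further data collection when consent to disclosure is also withdrawn.

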5.4 Adverse Event Reporting

The research coordinator will recommend that the participant contact their clinician for any worrisome concerns or symptoms.

The study team will be responsible for initiating the Serious Adverse Event (SAE) reporting process if the reported patient concern is an SAE. See Section 9.0.

5.5 Reasons for Withdrawal

Participants may be withdrawn from the study for the following reasons:

1. Participant desires withdrawal (reasons for withdrawal will be recorded); and
2. Study investigator(s) deems it in the participant's best interest to be withdrawn (reason for withdrawal recorded).
3. Participant decides to pursue a different dietary plan that conflicts with study

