5.5.1 Handling of Withdrawals

If the participant requests to be withdrawn from the study, they will be given appropriate treatment, but will not continue with scheduled study follow-ups. If the participant withdraws from the study and withdraws consent for disclosure of future information, no further evaluations will be performed and additional data will not be collected. The investigators may retain and continue to use data collected before withdrawal of consent.

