8.2 Study Feasibilities Measures

We will assess willingness to randomize as the number of eligible patients that randomized divided by the number of eligible patients (Aim 1). We will provide descriptive statistical summaries of time to complete survey materials, time interacting with the USDA Med-style Food Pattern platform, and changes in estimated weekly meal expenses. These data will be used to inform the future large-scale trial including the number of study sites, recruitment rate/study duration and amount of coordinator effort. The rate of willingness to randomize is unknown but as long as it is at least 20% our study will be successful. We would also want at least 50% of those willing to randomize to be willing to give a blood sample and at least half of those to give stool.

8.3 Treatment Fidelity and Adherence:

The Fred Hutch FFQ is a standard method of dietary intake assessment that has been used in several large-scale cohort studies including the Women’s Health initiative.^{153, 154} The degree of adherence with the USDA Healthy Med-style Food Pattern (Aim 1) will be ascertained by assigning point scores based on the estimated daily amounts of the recommended food groups and subgroups habitually consumed. Full points will be awarded to diets that meet all the

recommendations and partial points to diets that do not. Given that the USDA Healthy Med-style Food Pattern provides recommended amounts for relevant food groups, the adherence score will be based on food consumption data normalized per 100 kcal, much along the lines of the Healthy Eating Index (HEI). The HEI is a 100-point score that measures adherence to the DGA and is the standard measure of diet quality in the US. This approach represents an advance over the 14-item food frequency MEDAS score, which ranks adherence to the Med-style diet pattern using 3 cutpoints: ≤ 7 , 8–9, or ≥ 10 (maximal adherence).¹⁴⁵ The data derived will help us understand the central tendency and variability in Med-style food pattern scores which is critical for determining the sample size of a future trial. Degree of adherence to the different aspects of the medical management regimen will also be used to define per-protocol analysis and be considered as potential mediators and/or effect modifiers in explanatory regression models

8.4 Signal Assessment for Biomarkers:

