8.7 Sample Size and Statistical Power

Using 2:1 randomization, we will enroll 50 patients into a USDA Med-style Food Pattern and 25 patients to receive standardized guidance on fiber intake. The analytic aim of this study is to inform potential effect sizes and variance estimates toward the ultimate goal of conducting a definitive phase 3 randomized trial. While 1:1 randomization is more statistically efficient when group variances in outcome are similar, we plan to enroll more participants into the USDA Med-style food pattern intervention to strengthen the precision of estimates of adherence and patient-reported response. Since statistical testing will not be formally conducted, statistical power was not a primary motivation for sizing for this pilot study.¹⁶⁶ However, enrollment of 50 study participants in the USDA Med-style Food Pattern intervention allows a 95% one-sided confidence interval for the intervention adherence rate to exclude rates less than 0.70 if the observed adherence rate is 0.80 or higher in this pilot study.

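### Section 5.5 lets a diet switch end study participation in either arm and 5.5.1 does not secure follow-up afterwards, so primary-outcome FFQ scores can be lost for a reason likely related to adherence

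*Combined protocol and SAP*

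**What the plan says.** Section 5.5 opens with "Participants may be withdrawn from the study for the following reasons" and gives three reasons. The first is the participant's wish, the second is the investigator's view of the participant's best interest, and the third is "Participant decides to pursue a different dietary plan that conflicts with study". The third is not limited to one arm. It concerns leaving the study, not only leaving the diet.

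Section 5.5.1 covers two situations. For a requested withdrawal it says: "If the participant requests to be withdrawn from the study, they will be given appropriate treatment, but will not continue with scheduled study follow-ups". Where a participant also withdraws consent to future disclosure, no further data are collected. It does not say what follows when reason 3 is applied to someone who has not asked to leave.

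Table 2 in section 6.1 makes the FFQ-based Med-style score (baseline, 6 and 12 months) and retention (3, 6, 9 and 12 months) primary outcomes. Section 8.3 wants the score data for their "central tendency and variability in Med-style food pattern scores which is critical for determining the sample size of a future trial". Section 8.7 justifies 2:1 allocation by the wish to "strengthen the precision of estimates of adherence and patient-reported response". Section 8.6 states that "prevention of missing data is preferable to any attempted analysis correction". It then plans 10-fold multiple imputation as the primary approach, inverse probability weighting, and this: "We will also impute missing data under both pessimistic and optimistic scenarios".

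**The concern.** Taking up a conflicting diet is likely to be related to the quantity that the primary adherence outcome measures. A rule that lets this event end participation can remove the measurement for a reason connected with its value. The same event then also counts against retention, so the pilot could not cleanly separate people who left the diet from people who left the study. Those are different problems for the design of the larger trial: one concerns the intervention and the other concerns follow-up.

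The centre and spread of the food pattern score are also at stake, because the plan wants them for sizing the next trial. Participants who abandon the assigned diet inform both. Reasons 1 and 2 already cover people who wish or need to leave, so the loss under reason 3 is avoidable.

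**Working it through.** **Inputs.** Med-style arm 50, fiber arm 25, total 75 (8.1, 8.7). Follow-up FFQs at months 6 and 12 (Tables 1 and 2). Target in 8.7: an observed adherence rate of 0.80 in 50 participants, with a one-sided 95% limit excluding rates below 0.70. The number of switchers is not given.

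**1. The plan's own figure.** The Wald lower limit at 40/50 is 0.80 − 1.645 × √(0.80 × 0.20 / 50) = 0.80 − 0.093 = 0.707. The statement in 8.7 is reproduced, with 0.707 − 0.700 = 0.7 points to spare. It holds in the Wald form only narrowly: the Wilson limit is 0.693 and the Clopper-Pearson limit is 0.684.

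**2. What happens to a switcher, read from the text.**

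| How the switch is handled | Rule in 5.5.1 | Later FFQs |
|---|---|---|
| As a participant request | Scheduled follow-up stops | Lost |
| As withdrawal under reason 3, no request | None stated | Undetermined |
| Participant also withdraws consent to disclosure | No further data | Lost, properly |
| Discretion in 5.5 not used | Not applicable | Kept |

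So loss is possible but not certain, and it depends on how staff classify the event.

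**3. Cost per participant withdrawn with follow-up ended.** This assumes that the person would otherwise have stayed and responded.

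- FFQs: a switch before month 6 loses two of two follow-up scores. A later switch loses one of two.
- Retention at 12 months: 1/50 = 2.0 points in the Med-style arm, 1/25 = 4.0 points in the fiber arm, and 1/75 = 1.3 points overall.

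**4. What cannot be computed.** The direction and size of any bias in the score or rate would need the switch rate, the switchers' FFQ scores, the imputation predictors and, for a rate, the cut-off between adherent and not adherent. The documents give none of these.

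**The case against.** The strongest case against runs as follows. Withdrawal under 5.5 is permissive. Section 8.3 defines adherence as a graded FFQ score, not as a diet label, and section 2.1 notes that the Mediterranean diet shares features with other healthy patterns. A switcher could therefore still score well. In the fiber arm, a move towards a Mediterranean diet is contamination, not Med-style non-adherence. Section 8.6 has a full missing-data strategy. Section 5.2.7, written about survey burnout, already tells staff to prefer missed responses to withdrawal and to prioritise the FFQ.

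Most of this stands, and it limits the point to a possible loss of data with no stated bias. It does not remove the point. Imputation and weighting work from observed data and do not by themselves correct a loss driven by unobserved adherence. The pessimistic and optimistic scenarios are not defined. Continued collection would avoid the problem.

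Three stronger readings are tempting and are not supported:

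- *That 5.5 contradicts 8.3, 8.6, 8.7 or 9.1.* These sections favour keeping the data, and 8.3 handles low adherence in the analysis, since degree of adherence "will also be used to define per-protocol analysis". None of them conflicts with a permissive withdrawal rule. Section 9.1 monitors SAEs over the surveillance period without saying whether that period continues after withdrawal.
- *That a few losses would carry a poor adherence rate past 0.70.* If five switchers were all non-adherent and unobserved, 36/50 = 0.72 (Wald limit 0.616) would show as 36/45 = 0.80 (limit 0.702). That is a complete-case figure with an assumed number of switchers and an undefined cut-off. The planned primary approach is multiple imputation.
- *That clinical events are necessarily lost too.* Section 5.3 has record review triggered by a diverticulitis event, and the documents do not say whether it stops after reason 3.

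**Conclusion.** The point holds as a minor one: a stated rule permits an avoidable loss of primary-outcome data, in either arm, for a reason likely related to adherence, and the handling section does not prevent it. The supportable size is one or two follow-up FFQs per switcher and, for each Med-style participant, 2.0 points of that arm's 12-month retention. This rests on three conditions: the discretion is used, follow-up then ends, and the participant would otherwise have stayed and responded.

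No direction or size of bias is claimed. If few participants switch, the effect is small. The point does not invalidate the pilot; it is a cheap improvement.

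**What to change.** **Protocol.** Remove the diet switch as a ground for leaving the study in 5.5. Record it as *off assigned diet, remains in follow-up*. Continue FFQs, surveys and specimens in both arms unless the participant declines or withdraws consent. State in 5.5.1 which assessments continue after each withdrawal reason.

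**Analysis.** Report diet switching separately from loss to follow-up. Analyse every FFQ score obtained, whether or not the participant switched. Include the documented switch as a predictor in the 8.6 imputation model. Switchers without a later FFQ should not simply be counted as non-adherent: that would depart from the planned multiple imputation and would need a cut-off that the plan does not define.

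**Cost.** One protocol line, a clarification in 5.5.1 and a few SAP sentences. A few off-diet participants continue assessments, and reported adherence may be slightly less favourable. The change concerns data collection only and sets no dietary or clinical rule.
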